**Formal Title: Support, Educate, Empower: The SEE Personalized Glaucoma Coaching Trial**

**Working Title: The SEE Program**

**HUM00188154**

## **BACKGROUND AND SIGNIFICANCE**

Despite evidence from randomized clinical trials that medication reduces vision loss from glaucoma, it remains the second leading cause of blindness in the United States. A critical barrier to preventing vision loss is that about one-half of glaucoma patients are essentially “untreated” because they do not adhere to their medications. Ineffective self-management behaviors and poor clinical outcomes disproportionately affect the most vulnerable members of US society. There are programs individualized to use techniques such as tailored health communication and motivational interviewing for a wide range of chronic diseases.

**(HUM00112614)** We developed and pilot tested the The eyeGuide program to offer personalized counseling and education to patients who are poorly adherent to their glaucoma medications as part of their ophthalmic care. In addition, my team developed and pilot tested a glaucoma-specific motivational interviewing training program for ophthalmic para-professional staff. In the eyeGuide program, a trained glaucoma coach uses a web-based application to deliver personalized high-quality, counseling and education.

Our overall objective is to test whether the Support, Educate, Empower: (SEE) Personalized Glaucoma Coaching Program, compared to enhanced standard care by the physician with additional written education materials, improves glaucoma eye drop adherence through a randomized clinical trial among approximately 230 glaucoma patients with poor adherence at enrollment. We will recruit from clinics that serve low-income and minority populations as these populations have a higher incidence of both poor adherence and outcomes from glaucoma.

Our central hypothesis is that glaucoma patients with poor adherence who receive motivational-interviewing based counseling and personalized education from a trained non-physician glaucoma coach through the SEE Program will improve their medication adherence. In the six-month SEE Program, health educators trained as glaucoma coaches use an eHealth program as a tool to deliver personalized education (e.g. based on each person's diagnosis, test results, physician's recommendations) and motivational interviewing-based counseling to guide patients to identify their barriers to optimal adherence and brainstorm solutions. Additionally, participants can choose any or all of their preferred modalities for receiving reminders when a medication dose is missed: an alarm (light or sound), an automated phone call or text message.

## **OBJECTIVE**

Our overall objective is to test whether the SEE Program, compared to enhanced standard care, improves medication adherence through a randomized clinical trial among glaucoma patients with poor medication adherence at enrollment.

## **SPECIFIC AIMS**

- 1. Compare the efficacy of the SEE Program with enhanced standard care.** We will compare the intervention group to the enhanced standard care group to determine the intervention group will: a) have greater medication adherence over six months; b) have larger decrease in mean glaucoma-related distress; and c) have greater improvement in mean intraocular pressure.
- 2. Identify moderators and mediators of SEE Program effectiveness.** a) Given the higher prevalence of blinding glaucoma among African Americans and those with low incomes, it is important to assess the program effectiveness in those groups, so we will determine if there is an interaction between treatment and race/income; we will also assess whether there is an interaction effect by sex. b) Using the theoretical frameworks of Self Determination Theory and Empowerment Theory, we hypothesize that the SEE Program will improve autonomous motivation alongside improving autonomy support, competence, and satisfaction with care. The mediating effects of these factors on improving adherence will be measured.
- 3. Optimize the SEE Program for clinical dissemination using a mixed-methods evaluation of barriers and facilitators to implementation.** Using an integrated framework of the Reach, Effectiveness, Adoption, Implementation and Maintenance (RE-AIM) model and the Consolidated Framework for Implementation Research (CFIR), we will interview participants, glaucoma coaches, and key stakeholders to optimize the program. The results will inform future large-scale intervention implementation studies.

## METHODS

### **Specific Aim 1: Compare the efficacy of the SEE Program with enhanced standard care in improving glaucoma medication adherence.**

In Aim 1, we will test the efficacy of the SEE Program to improve medication adherence among glaucoma patients. Our study design is a randomized controlled clinical efficacy trial with an embedded mixed methods analysis. The primary outcome, medication adherence at six months, will be assessed objectively with electronic monitoring. We will test the efficacy of the intervention on improving medication adherence behavior while gathering data that will inform future program dissemination and implementation. We will conduct a parallel, two-armed RCT, recruiting participants (n=230) with self-reported poor adherence in equal numbers from two southeastern Michigan-based health systems {University of Michigan (UM) and Henry Ford (HF)}; that both serve low-income, minority populations. We will oversample African Americans to comprise at least 25% of our sample to ensure adequate power to assess improvements in this sub-population. We will enroll up to 160 participants at UM or HF. We will stop enrollment when the goal of 230 is met combining UM and HF.

We chose to work in two health systems to ensure adequate recruitment of patients who are poorly adherent to their medication and willing to participate.

The study will evaluate whether increasing glaucoma self-management support by having trained health educators provide MI-based counseling and personalized education, facilitated by an eHealth tool, improves medication adherence. We will use mixed methods (i.e., the collection, analysis, and combining of both quantitative and qualitative data) to investigate

elements important for future program implementation and dissemination. Specifically, we will use an “embedded” mixed methods design that involves collecting qualitative data during the intervention to better understand the mechanisms influencing implementation and outcomes. We will gather data on how patients, glaucoma coaches, ophthalmologists, optometrists and key eye clinic administrative personnel experience the intervention. The qualitative data combined with the trial results will drive our refinement of the intervention. This approach will ensure that the intervention has the greatest possible likelihood of future adoption should we find it has positive effects on processes and outcomes of care. The proposed study duration is five years, to allow for patient recruitment, completion of the six-month SEE Program, assessment of outcomes, and quantitative and qualitative data analysis.

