database. Following completion of the program, pharmacy refill data will be collected for an additional 12 months to assess longer-term effects of the SEE Program.

Randomization: After baseline testing, participants will be given their randomization assignment. We will use block randomization stratified by site to allocate participants to the intervention or control groups. A randomization list using blocks of varying sizes (2, 4, and 6) will be produced in TATUM for each site. Block randomization maintains approximate group size balance during the trial. Varying the block size lowers the likelihood of knowing the group assignment of the next eligible participant. Randomized group status will be available to the research associate by email after baseline information and consent are entered into REDCap and eligibility is confirmed.

Retention strategies: Participants receive incentives: \$25 for each completed study visit and \$10/month for six months for using the electronic adherence monitor during the trial. The coaching program will be delivered free of charge. Participants randomized to the control arm will have the opportunity to schedule a free coaching session after completing all follow-up assessments. Participants will be given \$15 to defray travel costs for each study visit. If a participant has no other means of transportation and lives within 10 miles of the clinic, transportation will be arranged instead of the travel reimbursement.

The research associates will make multiple attempts to re-schedule missed appointments within a one-month window. We will also employ a combination of retention strategies, including pre-appointment reminder calling, phone follow-up of missed appointments, updating of contact information at each visit, and distribution of materials with study phone numbers. Participants will receive a birthday card mailed to their address from the study team.

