### **Sample Size Aim 1: Compare the efficacy of the SEE Program with enhanced standard care in improving glaucoma medication adherence.**

We conducted brief interviews with 25 glaucoma specialists from throughout the US to gauge expert opinion regarding clinically important effect size. Their average recommendation for difference of group proportions of good adherence was 18.5 percentage points (95% CI 15.6-

21.5). Their average recommendation for difference of group mean adherence was 17.7 percentage points (95% CI 14.6-20.8). Additionally, mean medication adherence increased by 20 percentage points in our SEE Program pilot study from 65.7% ( $\pm 10.3$ ) at baseline to 85.7% ( $\pm 11.8$ ) after the program. With 97 participants in each group, a t-test has 80% power to detect a difference of 8 percentage points in mean adherence between the two groups, if the within group standard deviation (SD) is 20 ( $0.40 \times 20 = 8$ ). In our preliminary data the SD was 18, but we anticipate and plan for a possibly more diverse study group (calculated using R 'pwr' package). Our glaucoma specialists were divided on the importance of clinically important effect size, so we plan to be adequately powered for both continuous and binary adherence measures. Their average recommendation for difference of group proportions of good adherence was 18.5 percentage points (95% CI 15.6-21.5). The proposed sample size (n=97 per group) provides 80% power (at two-sided  $\alpha=0.05$ ) for Pearson's Chi Square Test of Independence to find a difference of 20 percentage points for the proportion of patients attaining good ( $\geq 80\%$ ) adherence between the intervention and control groups.

For our secondary outcome, with this sample size, we can detect a 1.1-point difference in mean change in Glaucoma Related Distress (scale 6-18) between trial arms if the SD is 2.8, as it was in our preliminary data. For this sample size in our exploratory outcome, we can detect a 1.9 mmHg difference in mean change in IOP between trial arms if the SD is 4.6 mmHg, as it was in our preliminary data. Although we will make concerted efforts to maximize retention, we will prepare for up to a 20% loss to follow-up as was experienced in our preliminary study and will enroll 115 participants in each arm for a total of 230 participants.

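### The 25% African American floor is said to give adequate power in that group with no effect size stated; it gives 80% power only for about 15 to 16.5 points, and the related interaction example does not reach its stated R² increase.

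*Combined protocol and SAP*

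**What the plan says.** The protocol's Specific Aim 1 paragraph under METHODS gives the reason for the recruitment floor: "We will oversample African Americans to comprise at least 25% of our sample to ensure adequate power to assess improvements in this sub-population". It states no effect size, test or power figure for that group.

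Sample Size Aim 1 sizes the main comparison: "With 97 participants in each group, a t-test has 80% power to detect a difference of 8 percentage points in mean adherence", "if the within group standard deviation (SD) is 20". It adds a smaller observed value: "In our preliminary data the SD was 18". On recruitment it says "we will prepare for up to a 20% loss to follow-up" and that the trial "will enroll 115 participants in each arm for a total of 230 participants". The same section reports the specialists' average recommendation of 17.7 points for the difference in mean adherence (95% CI 14.6 to 20.8) and a 20-point before-to-after rise in the pilot.

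Sample Size Aim 2 mentions the oversampling again, this time for the moderator analysis. It claims power for a 4-percentage-point increase in R², illustrated by a rise from 60% to 70% in Whites and from 50% to 75% in African Americans.

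Race is not a randomization stratum: "We will use block randomization stratified by site to allocate participants".

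**The concern.** The sentence sits under the efficacy aim, and its plain meaning is power to show that SEE improves adherence among African American participants. A quarter of the sample cannot have the power of the whole for the same difference, and no section names a larger difference for this group. Sample Size Aim 2 does not fill the gap, because an interaction test asks whether the effect differs by race, not whether African American participants benefit.

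The Specific Aims single this group out because of its higher prevalence of blinding glaucoma, so readers will look for a result there. They need to know how large an effect the floor can detect and how wide the interval will be. Without that, an unqualified statement of adequacy gives no guidance on reading an inconclusive estimate.

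**Working it through.** **Inputs.** From Sample Size Aim 1: 97 evaluable per arm, 8 points, SD 20 (18 as sensitivity), 115 enrolled per arm, up to 20% loss. From Specific Aim 1: a 25% floor. Two-sided α of 0.05 is stated for the binary outcome in the same section and assumed here for the t-test. An equal split of African American participants between arms is also an assumption.

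**Step 1: reproduce the plan's figure.** For two means, SE = SD × √(2/n) and the noncentrality is difference/SE. With n = 97 and SD 20, SE = 20 × √(2/97) = 2.87, and 8/2.87 = 2.79. The noncentral t gives 79.2% power (normal approximation 79.6%). The stated 80% reproduces.

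**Step 2: the same test at the floor.** 0.25 × 97 = 24.25, about 24 per arm. SE = 20 × √(2/24) = 5.77, and 8/5.77 = 1.39, giving 27% power. The 95% CI half-width is 2.013 × 5.77 = 11.6 points. If all 230 are analysed, 0.25 × 115 = 28.75, about 29 per arm. SE is then 5.25, power 32%, and half-width 2.003 × 5.25 = 10.5 points.

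| African American n per arm | SD | Power for 8 points | Difference with 80% power |
|---|---|---|---|
| 23 (20% lost from 115) | 20 | 26% | 16.9 |
| 24 (of 97) | 20 | 27% | 16.5 |
| 29 (of 115) | 20 | 32% | 15.0 |
| 24 (of 97) | 18 | 33% | 14.9 |
| 29 (of 115) | 18 | 38% | 13.5 |

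**Step 3: larger effects, 24 per arm, SD 20.** Power is 40% for 10 points, 70% for 14.6 (the lower confidence limit of the specialists' figure), 85% for 17.7, and 92% for 20.

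**Step 4: the interaction statement in Sample Size Aim 2.** Taking an R² increase of 0.04 with nothing else explained, f² = 0.04/0.96 = 0.0417. With N = 194 the noncentrality is 0.0417 × 194 = 8.08. The F test (1 df, three model terms) has about 81% power, so the headline figure holds.

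**Step 5: the worked example.** The effects are 10 and 25 points, so the interaction contrast is 15. With half the sample per arm and a quarter African American:
- Interaction variance = 15² × 0.25 × (0.25 × 0.75) = 10.55.
- The cell means 60, 70, 50 and 75 carry weights 0.375, 0.375, 0.125 and 0.125. Their mean is 64.375 and the total between-cell variance is 58.98.
- R² increase at SD 20 = 10.55/(58.98 + 400) = 2.3%. Here f² = 10.55/400 = 0.0264 and power is 61%.
- R² increase at SD 18 = 10.55/(58.98 + 324) = 2.8%, with 71% power.
- If 20 is taken as the total SD, the increase is 10.55/400 = 2.6%.
- For the example to reach 4%, total variance would have to be 10.55/0.04 = 263.7. That implies a within-cell SD of √(263.7 − 58.98) ≈ 14.3, below both SDs in the plan.

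**The case against.** The best reply has four parts.

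First, the Specific Aims and Sample Size Aim 2 route assessment by race through an interaction term, so the Aim 1 sentence may be loose shorthand for that analysis. This is plausible, and it is one way to repair the text. It does not rescue the sentence as written, because the interaction answers another question and its own example falls short of 4%.

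Second, no section sets 8 points as the target within African American participants. This stands. A reader might infer that the trial is underpowered in this group for any effect of interest, and the documents do not support that: power is 85% for 17.7 points and 92% for 20. Against this, the 20 points is a within-person pilot change rather than a difference between arms, and the main comparison is itself sized on 8.

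Third, 25% is a minimum. This also stands, but the sentence says the floor will ensure power, so the floor is the case to test.

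Fourth, the Statistical Analysis Plan specifies no treatment test within race. A reader might infer that a non-significant result there would be reported as an adequately powered negative. No text describes such a test or reporting rule, so that inference should not be drawn.

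**Conclusion.** The point holds as a defect in a stated design justification. At the 25% floor the within-group comparison has 80% power for about 16.5 points (15.0 if nobody is lost) and 27% (32%) for 8 points. No combination of the plan's own sample sizes and SDs at the floor lifts power for 8 points above 38%. The adequacy claim is true only for effects near the specialists' 17.7 points, and the plan does not say so. Separately, the interaction example corresponds to an R² increase of 2.3% to 2.8%, not 4%, at the plan's SDs.

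These results assume an equal split of African American participants between arms, the overall SD within that group, two-sided α of 0.05, and no covariate adjustment. Adjustment for predictors of adherence, which Aim 2 intends, could raise the interaction power. It would not by itself raise the example's R² increase, which is measured against total variance. The primary analysis and its sample size are not affected.

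**What to change.** 1. In Specific Aim 1, replace the adequacy clause in one of two ways. Either state what the floor delivers: 80% power for a difference of about 15 to 16.5 points in African American participants, 27% to 32% power for 8 points, and a 95% CI half-width of about 10.5 to 11.6 points at SD 20. Or limit the clause to the treatment-by-race interaction and refer to Sample Size Aim 2.
2. In Sample Size Aim 2, correct the example or the R² figure so that they agree, and state the SD used.
3. Add one sentence: any estimate in African American participants is reported with its confidence interval beside the overall effect, and a non-significant result is not read as lack of benefit.

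The cost is wording only. Recruitment, randomization and the primary analysis do not change.

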**Specific Aim: 2 Identify moderators and mediators of SEE Program effectiveness.**

The primary moderator we will assess is income (below the federal poverty line or not). We will also assess whether race (African American or not) and sex (male or female) moderate (interact with) the effect of the SEE Program on medication adherence. The primary moderator of treatment effect (income) will be assessed with an interaction term added to a linear regression model of continuous medication adherence, adjusted for known confounders of adherence.

**Specific Aim 3: Optimize the SEE Program for clinical dissemination using a mixed-methods evaluation of barriers and facilitators to implementation.**

In Aim 3, we will gain an in-depth understanding of participant experience in the SEE Program and of health system key stakeholders’ opinions on barriers and facilitators to implementation. Together, Aims 2 and 3 will give us a quantitative and qualitative evaluation of the SEE Program that will enable future program optimization through improved tailoring, more efficient protocols and opportunities to streamline the intervention. At the completion of these Aims, we will have developed a tool kit of all training and intervention materials to guide dissemination efforts in implementing better self-management support to improve glaucoma outcomes.

**Rationale for the Intervention**

Both empowerment theory and self-determination theory form the basis for our medication adherence intervention. The World Health Organization describes empowerment as a “process through which people gain greater control over decisions and actions affecting their health.” Empowerment is particularly important for people who may experience a powerlessness that can come with minority status or poverty. In order for people to best manage their eye health, empowerment theory suggests that they must be supported to develop knowledge and skills to care for their health, coping skills for managing emotions that can negatively affect self-management, and motivation to improve health. Self-determination theory posits that to change a health behavior, people must feel autonomously supported and connected to their health care provider, perceive that they are competent to engage in the behavior, and be motivated to improve.

The application of MI in our study is consistent with the underpinnings of both theoretical frameworks. MI counseling engages patients by discussing priorities and obstacles to facilitate intrinsic motivation— personally compelling reasons— to change health behavior. Recent

Cochrane reviews and meta-analyses of medication adherence interventions found that MI-based counseling was the most successful approach to increasing adherence across many chronic diseases. We hypothesize that using MI-based personalized glaucoma counseling and education will increase participants' motivation, competence, and satisfaction with care, thereby increasing medication adherence and decreasing glaucoma related distress.

## **RESEARCH DESIGN**

### **Recruitment:**

Participant selection will occur from the UMHS and HFHS electronic health records. We will generate a list of all patients at UM and HF taking  $\geq 1$  ocular hypotensive medication with a diagnosis of any kind of glaucoma, suspected glaucoma or ocular hypertension who are  $\geq 18$  years of age. A letter will be sent to all potentially eligible participants allowing people to opt out of phone based recruitment.

### Inclusion criteria:

$\geq 18$  years of age

Taking  $\geq 1$  ocular hypotensive medication with a diagnosis of any kind of glaucoma, suspected glaucoma or ocular hypertension.

Did not opt-out from recruitment letter.

Able to instill eyedrops themselves.

Have a phone- cell or landline.

### Exclusion criteria:

Do not speak English

Have a diagnose serious mental illness (defined as schizophrenia, bipolar disorder, or a major depressive episode with psychotic features)

Diagnosed cognitive impairment

Do not instill their own eye drops

Had laser or incisional glaucoma surgery within the last 3 months or scheduled during the six-month study period

Prisoners

Active uveitis or ocular infection

Participated in pilot study

Unable to attend all study visits

\*We will recruit men and women equally. We will oversample African American patients to ensure at least 25% representation in the trial sample.

UM Study staff will become registered Henry Ford Health Systems volunteers. Henry Ford staff will become registered as UM volunteers. This will allow for staff to access clinic space and electronic health records at each institution.

At UM and HF, research associates will call potential participants and obtain verbal consent to give a survey assessing self-reported medication adherence to determine study eligibility. Self-reported medication adherence will be measured from a single question asking “Over the past month, what percentage of your drops do you think you took correctly?” Those who self-report <85% adherence will be invited to participate in the study. Research associates will schedule a baseline visit to complete the informed consent process, the baseline survey, measurement of intraocular pressure and measurement of visual acuity and visual fields if participants have not had a reliable test with the last year(HVF SITA 24-2, ≤20% fixation losses, ≤15% false positives).

**Participant Assessments:** After eligibility has been confirmed and informed consent has been obtained, prior to randomization, a research associate will measure participants’ intraocular pressure (IOP), record socio-demographic characteristics, administer a baseline survey including measures of glaucoma-related distress, glaucoma knowledge, perceived competence, motivation, self-efficacy, and autonomy support from their eye care team. IOP measurements will be taken at all in-person study visits. Surveys will be administered by study staff on a tablet with the ability to enlarge the font or have the survey read out loud. Eye drop instillation will be video-recorded. Additionally, we will use commercially available inertial measurement unit sensors (Xsens-dot, Movella, Netherlands) to assess the kinematics of all eye drop instillations. The sensor will be attached to the bottom of the artificial tear by a custom made silicone sleeve and will not interfere with the dispensing of the artificial tears. Snellen visual acuity will be recorded on all participants. Humphrey visual field testing (SITA Fast, 24-2) will be performed on participants who have not had a reliable visual field (SITA, 24-2) within the last year. Participants will be randomized to the SEE Program (experimental) or enhanced standard care by the physician with additional written education materials (control). Medication adherence will be monitored electronically for all participants from baseline through the end of the 6-month program period. A baseline measure of medication adherence will be obtained by an objective method (medication possession ratios assessed from pharmacy refill data for six months prior to study participation) and subjective method (survey). After six-months, a research associate will video-record eye drop instillation, administer a survey with the same behavioral and psychosocial measures and a quantitative program evaluation, and then a masked research associate will measure IOP and conduct a 15-30 minute semi-structured interview with participants in the SEE Program arm to assess their experience with the program. Additionally, we will call participants that do or did not return for the exit visit to ask if they will complete the exit surveys over the phone. All data will be entered into the REDCap

---

database. Following completion of the program, pharmacy refill data will be collected for an additional 12 months to assess longer-term effects of the SEE Program.

Randomization: After baseline testing, participants will be given their randomization assignment. We will use block randomization stratified by site to allocate participants to the intervention or control groups. A randomization list using blocks of varying sizes (2, 4, and 6) will be produced in TATUM for each site. Block randomization maintains approximate group size balance during the trial. Varying the block size lowers the likelihood of knowing the group assignment of the next eligible participant. Randomized group status will be available to the research associate by email after baseline information and consent are entered into REDCap and eligibility is confirmed.

Retention strategies: Participants receive incentives: \$25 for each completed study visit and \$10/month for six months for using the electronic adherence monitor during the trial. The coaching program will be delivered free of charge. Participants randomized to the control arm will have the opportunity to schedule a free coaching session after completing all follow-up assessments. Participants will be given \$15 to defray travel costs for each study visit. If a participant has no other means of transportation and lives within 10 miles of the clinic, transportation will be arranged instead of the travel reimbursement.

The research associates will make multiple attempts to re-schedule missed appointments within a one-month window. We will also employ a combination of retention strategies, including pre-appointment reminder calling, phone follow-up of missed appointments, updating of contact information at each visit, and distribution of materials with study phone numbers. Participants will receive a birthday card mailed to their address from the study team.

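### Masking at exit is stated only for the exploratory IOP reading, not for the survey that carries the secondary distress outcome and the Aim 2 mediators

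*Combined protocol and SAP*

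**What the plan says.** The exit visit is described under Participant Assessments in the Research Design. One sentence assigns two roles. First, "a research associate will video-record eye drop instillation, administer a survey with the same behavioral and psychosocial measures and a quantitative program evaluation"; next, "and then a masked research associate will measure IOP and conduct a 15-30 minute semi-structured interview with participants in the SEE Program arm". The word masked is used nowhere else in the document.

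The exit survey repeats the baseline measures. At baseline the associate is to "administer a baseline survey including measures of glaucoma-related distress, glaucoma knowledge, perceived competence, motivation, self-efficacy", and autonomy support from the eye care team is also listed. The exit survey therefore contains glaucoma-related distress together with motivation, competence and autonomy support, which Specific Aims lists among the Aim 2 mediators.

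On mode, "Surveys will be administered by study staff on a tablet with the ability to enlarge the font or have the survey read out loud". Participants who miss the exit visit may be called and asked to complete the surveys by phone. No masking is stated for any of these modes.

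Outcomes ranks distress as secondary and IOP as exploratory. The Statistical Analysis Plan regresses exit distress on treatment group, adjusting for baseline distress and clinic. The Randomization paragraph says "Randomized group status will be available to the research associate by email" once baseline entry and the eligibility check are complete. The Sub-Study paragraph shows that a satisfaction survey about SEE is among the six-month exit surveys.

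**The concern.** Masking at this visit protects the outcome with less need of it. A tonometer reading leaves some room for observer influence; answers to questions about distress and motivation, given with staff present, leave more. If the person giving the survey knows the arm, help or prompting can differ between arms. If questions about the program come before the distress items, they can colour the answers of coached participants.

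Either effect would probably favour SEE on the secondary outcome and on the mediators. Baseline adjustment would not remove it: the baseline survey precedes randomization, so it cannot capture an arm-related difference that arises at exit.

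**Working it through.** **1. The passages side by side**

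| Item | Exit survey (distress, mediators) | Exit IOP |
|---|---|---|
| Rank (Outcomes) | Secondary, for distress | Exploratory |
| Who collects it (Participant Assessments) | A research associate | A masked research associate |
| Masking stated | No | Yes |
| How obtained | Self-report on a staff-administered tablet, possibly read aloud, or by phone | iCare tonometer, median of three readings |
| Order stated | None between the scales and the program evaluation | After the survey |

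The last row matters for the remedy. As written, IOP is read after the survey, and the masked associate also interviews SEE-arm participants only. That associate must therefore learn the arm during the visit, and the plan does not say that IOP is recorded before then.

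**2. The plan's own figure for distress**

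Inputs from Sample Size Aim 1: SD of change 2.8, 97 per arm, 80% power, two-sided alpha 0.05, stated detectable difference 1.1 points.

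- Standard error of the arm difference: 2.8 × √(2/97) = 0.402.
- Detectable difference: 0.402 × (1.960 + 0.842) = 1.126 by the normal formula, or 1.132 by the t-test. Both round to 1.1, so the stated figure is reproduced.
- Power at exactly 1.1 points is 78.1% (normal) or 77.7% (t-test).

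**3. Illustration of what a shift would do**

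The documents give no size for an administrator or ordering effect, so every shift b below is an assumption. The values 0.28 and 0.56 are 0.1 and 0.2 of the SD of 2.8. With no true effect, the two-sided rejection rate is

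1 − Φ(1.960 − b/0.402) + Φ(−1.960 − b/0.402).

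| Assumed shift b (points) | b/1.1 | b/0.402 | Rejection rate |
|---|---|---|---|
| 0.10 | 9% | 0.25 | 5.7% |
| 0.25 | 23% | 0.62 | 9.5% |
| 0.28 | 25% | 0.70 | 10.7% |
| 0.50 | 45% | 1.24 | 23.8% |
| 0.56 | 51% | 1.39 | 28.6% |

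These rates follow from the chosen shift. They do not separate the part that masking and ordering could prevent from the part due to participants knowing their own arm. No sample-size figure changes.

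**The case against.** A reader might infer that the survey is given by an unmasked associate who knows the arm. The documents do not say so. The contrast within the exit sentence suggests it, but the allocation email goes to the research associate after baseline, and nothing says that this person runs the exit visit six months later. The plan refers to research associates in the plural, across two sites. Only the weaker statement is supported: this associate is not stated to be masked.

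A reader might also infer that distress and the program evaluation form a single questionnaire. The sentence can be read that way, but the plan elsewhere speaks of exit surveys in the plural and names the SEE satisfaction survey separately. The psychosocial measures are also mentioned before the evaluation, although that is not an order rule. What stands is that no order is set.

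The strongest objection is that in a self-reported outcome the participant is the assessor, and participants know whether they were coached. Coaching is given by health educators trained as coaches, and nothing says that participants would identify the exit associate with the program. Reading aloud may be a function of the tablet. Much of any courtesy bias would survive masking of the administrator. This limits the benefit but does not remove the point: the plan already provides a masked person at this visit and does not use that person for the higher-ranked outcome.

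Finally, giving the survey to the masked associate before IOP could expose the arm in conversation and weaken the one masked measurement. That objection is sound, and it determines the order proposed under the fix.

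**Conclusion.** The point holds in limited form. Carried out as written, the plan leaves the secondary distress outcome and the Aim 2 mediators without stated masking of the administrator and without a set order against the program evaluation, while exploratory IOP has a masked assessor. This can be changed in the visit procedure and is more than a missing detail.

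The size of any bias is unknown. The range of about 6% to 29% for the error rate rests wholly on assumed shifts of 0.1 to 0.56 points, with the plan's SD and 97 per arm. It shows sensitivity and is not an estimate; at the low end the effect is close to nothing. Only part of any bias could be prevented, because participants know their arm. The primary outcome is measured by electronic monitors and is not touched.

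**What to change.** Amend Participant Assessments so that the exit visit runs in this order:

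1. The masked associate already planned measures and records IOP.
2. The same associate gives the distress scale, then the other psychosocial scales, self-completed on the tablet where possible. All are recorded before that associate learns the arm.
3. Only then does the other associate give the program evaluation, and the SEE-arm interview takes place.

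For exit surveys by phone, keep the same scale order and use a caller who has not been told the arm where existing staffing allows. State the masking status of whoever gives the survey in each mode. Acknowledge in the analysis plan that self-report bias from participants knowing their arm remains.

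The cost is a longer slot for the masked associate, a fixed order at the visit, and some chance that participants reveal their arm during the survey; by then IOP has been recorded. The in-person change uses roles already planned for the visit. A masked phone caller may need extra staff, since the plan describes a masked associate only at the exit visit.
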